3. METHODOLOGY

STUDY SITE

This study will be conducted within the malaria endemic regions of Nigeria. The study population will be enrolled at each of the following study sites located within the malaria endemic region of Nigeria;

1. University College Hospital, Ibadan
2. Amino Kano University, Kano
3. General Sani Abacha Specialist Hospital, Damaturu
4. State Specialist Hospital, Sokoto
5. Massey's Children Hospital, Lagos Island

STUDY DESIGN^[1-5]

This will be a prospective, pivotal, multi-center clinical study.

STUDY POPULATIONS

Study participants involved in this study will be children aged between 6 months and 12-year-old who have been diagnosed with cerebral malaria.

Inclusion Criteria:

- Children aged 6 months- 12 years admitted to any one of the study sites who satisfy the standard clinical case definition of cerebral malaria

- Blantyre coma score of ≤ 2
- Known results of a positive malaria test (blood smear or malaria rapid diagnostic test)
- Consent provided by parents/caregivers of the eligible children.

Exclusion criteria:

- Children admitted who satisfy the standard clinical case definition of cerebral malaria, but when there is no clinician/nurse available to do an examination within 6 hours of admission.

SAMPLING^[1-3]

Sample size determination

We aim to demonstrate MR detection performance on a validation dataset collected with continuous enrollment of clinically diagnosed CM patients with or without malarial retinopathy. About 61% of CM-diagnosed patients show a manifestation of CM in retina, in form of retinal lesions, called malarial retinopathy (MR) [xi,xii,xiii]. Rest 39% of CM-diagnosed patients do not exhibit MR. So, the prevalence of MR in CM-diagnosed patients is 61%.

The study hypothesis is that the sensitivity and specificity of detecting MR using ASPIRE's MR detection algorithm is non-inferior to the clinical reference standard, which is defined as the reading of retinal images for MR detection by ophthalmic specialists such as ophthalmologists.

Non-Inferiority test design:

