According to literature studies, the sensitivity and specificity of ophthalmologists in reading retinal images to detect retinal diseases are 89% and 87%, respectively [xiv]. We aim to demonstrate that the sensitivity and specificity of our software-based test are non-inferior to the ophthalmologist's standard, with 7% non-inferiority margin [xv]. Therefore, the lower-bound on both sensitivity and specificity will be at least equal or greater than the minimum sensitivity and specificity requirements for a diagnostic software as recommended by the FDA, of 80% and 80%, respectively.

The study will use a non-inferiority design and seek to demonstrate that the experimental method (software-based reading of retinal images) is not appreciably worse than the standard method (ophthalmologist's reading of retinal images). The reason behind using a non-inferiority design is that the proposed software-based test is not expected to be better than the standard test (ophthalmologist's reading of retinal images) on a primary efficacy end point in clinical study; but the availability, accessibility, affordability, and compliance of the proposed software-based test will be better outside the clinical study and hence efficacy will be better outside the study. Therefore, the proposed software-based test has potential to provide greater clinical benefit and/or outcome at the cost of being non-inferior in performance compared to the standard test [xvi].

In this study design, we used Blackwelder formula [xvii,xviii] to calculate sample size:

$$N_{cases} = \frac{(Z_\alpha + Z_\beta)^2}{(\pi_S - \pi_E - d)^2} \left[\pi_E(1 - \pi_E) + \frac{\pi_S(1 - \pi_S)}{\lambda} \right],$$

where

$$\lambda = \left(\frac{1 - Prev}{Prev} \right).$$

The conjectured accuracy (sensitivity/specificity) of the standard test is π_s , the conjectured accuracy (sensitivity/specificity) of the proposed diagnostic/experimental test is π_E . $Z\alpha$ and $Z\beta$ are standard values assuming 80% power and 5% Type-I error. "Prev" is prevalence of disease-positive patients, and "d" is a non-inferiority margin.

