A statistical calculator developed by the National Institutes of Health - National Cancer Institute (NIH-NCI) Statistics group [xix] (that implements Blackwelder's formula) was used to perform the sample size calculations. To verify the calculations, an "R-Studio" package was used that includes a function to calculate the sample size needed for two sample non-inferiority test. The R package is "epiR" and the function that performs sample size calculations is "epi.ssninfb()" [xx]. The documentation for this function also references the Blackwelder (1982) method used by the NIH-NCI Statistics group, and contains two examples illustrating how the function is used to perform sample size calculations for a non-inferiority study with a binary outcome measure.

Input parameters:

The input parameters required for sample size calculation are the expected response rates in each group (experimental and standard), non-inferiority margin, power, alpha, and prevalence of disease-positive (MR-positive) patients.

For our study, we propose to determine a sample size required to test our software-based test for MR detection for binary classification (“MR detected” or “MR not detected”). The conjectured sensitivity of the standard test is $\pi_s = 0.89$ (ophthalmologist’s sensitivity), and the conjectured sensitivity of the proposed experimental test is $\pi_E = 0.89$. At the noninferiority margin of $d = 0.07$, how many subjects should we include in the study to maintain 80% power and 5% Type-I error, while assuming the prevalence of Referral (MR-positive or MR detected) in the CM-diagnosed population to be 61%?

Results

The input parameters used to demonstrate the conjectured sensitivity of the experimental test of 0.89, yielded the sample size requirement as the minimum number of disease-positive “cases” of 318, and minimum number of disease-negative “controls” of 203. Using the same method, the input parameters used to demonstrate the conjectured specificity of the experimental test of 0.87, yielded the sample size requirement as the minimum number of disease-positive “cases” of 366, and minimum number of disease-negative “controls” of 234.

Conclusion

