To establish that our software-based test is non-inferior to the standard test (ophthalmologist’s reading of images), with sensitivity of 0.89 and specificity of 0.87; we will require a minimum number of disease-positive (MR-positive) “cases” of 366, and minimum number of disease-negative (MR-negative) “controls” of 234. In total, we will require a minimum sample size of 600 CM-diagnosed patients to validate our proposed test.

Once we enroll the minimum number of MR-positive and MR-negative patients required, we propose to validate the software-based test performance on the collected sample and verify if the resulting sensitivity/specificity is within the margin of difference. Upon verification, it can be concluded that the experimental test is non-inferior to the standard test within a non-inferiority margin of 7%.

Sampling procedure [11]

The procedure will be as follows:

1. Pupillary light response is checked and then pupils are dilated with 0.5% tropicamide and 10% phenylephrine, repeated after 10 minutes.
2. Ophthalmologist, clinician or nurse takes iNview photos (at least 8 photos: 4 optic disc center, 4 macula center)
3. Ophthalmologist, clinician or nurse takes VistaView photos (at least 8 photos: 4 optic disc center, 4 macula center)
4. Ophthalmologist, clinician or nurse takes Pictor-Plus photos (at least 8 photos: 4 optic disc center, 4 macula center)
5. The retinal photos captured by Pictor-Plus, VistaView, and iNview cameras may be transmitted to a laptop computer or smartphone automatically and analyzed instantaneously for image quality by a computer-based software. The software will either accept or reject each photo based on high or low image quality, respectively. A graphical display on a laptop computer or smartphone

will be shown to the imager (ophthalmologist, clinician, or nurse) that demonstrates the captured image and whether it was accepted or rejected.

6. The retinal photos captured by Pictor-Plus, VistaView, and iNview cameras will be analyzed instantaneously for detection of malarial retinopathy (MR) by a computer-based software. The imager (ophthalmologist, clinician, or nurse) will be masked to MR detection results due to non-interventional nature of this study.
7. The analysis of retinal photos for image quality and MR detection will be fully automatic and handled by a laptop computer or smartphone and will not require manual inputs or interference from the imager.
8. Ophthalmologist performs BIO when possible.

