The following conditions apply to the steps above:

- a) All the children will have the retinal images taken and when possible, a BIO (if available) conducted by an ophthalmologist as part of the study component.
- b) Fundus examination and photography will be done as soon as the pupils are a minimum of 6 mm or not more than 1-hour post dilation.
- c) The order of steps 2-4 can be interchanged or some of the steps can be omitted (depending upon camera availability) at the discretion of the ophthalmologist/clinician/nurse but once determined, efforts will be followed consistently with each patient.
- d) Ideally the examinations will take place within a few minutes of each other, but if this is not possible, no more than 2 hours between examinations will be accepted

(due to possibility of changes in the clinical features). The camera images are time stamped so that this can be verified.

- e) The data collection form will be the “standard form” used in previous studies of MR.

The retinal image data obtained using Pictor-Plus, VistaView, and iNview will be analyzed by an independent retinal grader masked to the ophthalmologist’s findings in the BIO exam.

EXAMINATION PROCEDURE FOR RETINAL CAMERAS (Pictor-Plus, VistaView, iNview)

The right eye will be examined first with slow “panning” in image mode of the disc, the macula, the horizontal raphe, along all four main vascular arcades, and a 360-degree survey outside the arcades. The left will be examined the same way. These procedures may have to be modified if the eyes are deviated or the head position is restricted due to intravenous catheter. Images collected by Pictor-Plus, VistaView, and iNview will be transmitted to a laptop computer or smartphone automatically and analyzed instantaneously for image quality by a computer-based software. The software will either accept or reject each photo based on high or low image quality, respectively. A graphical display on a laptop computer or smartphone will be shown to the imager (ophthalmologist, clinician, or nurse) that demonstrates the captured image and whether it was accepted or rejected. Further, the images will be analyzed instantaneously for detection of malarial retinopathy (MR) by a computer-based software. The imager (ophthalmologist, clinician, or nurse) will be masked to MR detection results. The images will be independently graded by a retinal grader masked to the BIO exam and clinical status. The user will

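### The sample-size formula uses the ratio of MR-negative to MR-positive children as the size ratio of two reader groups, so the stated 80% power belongs to neither sensitivity nor specificity, and the success rule names no confidence limit

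*Combined protocol and SAP*

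**What the plan says.** All of this is in 3. METHODOLOGY, Sample size determination, unless noted.

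- **Hypothesis.** The software's sensitivity and specificity are to be "non-inferior to the clinical reference standard, which is defined as the reading of retinal images for MR detection by ophthalmic specialists such as ophthalmologists".
- **Formula.** Under Non-Inferiority test design, the ophthalmologist's variance is divided by λ, and λ is set to (1 − Prev)/Prev. The Z values "are standard values assuming 80% power and 5% Type-I error"; sidedness is not given.
- **Inputs.** These are "the expected response rates in each group (experimental and standard), non-inferiority margin, power, alpha, and prevalence of disease-positive (MR-positive) patients". Both readers are taken at 0.89 for sensitivity and 0.87 for specificity, with a margin of 0.07 and MR prevalence of 61%. The checking software is described as a two-sample non-inferiority calculation.
- **Results.** The sensitivity run gives 318 cases and 203 controls. For the other run, "the input parameters used to demonstrate the conjectured specificity of the experimental test of 0.87, yielded the sample size requirement" of 366 cases and 234 controls. Cases are defined as MR-positive children and controls as MR-negative.
- **Conclusion.** "In total, we will require a minimum sample size of 600 CM-diagnosed patients to validate our proposed test".
- **Success rule.** After enrolment the team will "verify if the resulting sensitivity/specificity is within the margin of difference", and non-inferiority then follows.
- **Bound.** Non-Inferiority test design also says: "Therefore, the lower-bound on both sensitivity and specificity will be at least equal or greater than the minimum sensitivity and specificity requirements", citing 80% and 80%.
- **DATA ANALYSIS.** Sensitivity and specificity are to be reported with 95% confidence intervals. Nothing there mentions the 7% margin. The list of comparisons at that point is incomplete in the text available for review.

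**The concern.** In a two-group formula of this kind, the quantity dividing the standard group's variance is the size of that group relative to the experimental group. Here the groups are readers (software and ophthalmologist), not disease states. Filling λ with a prevalence ratio turns a reader-group ratio into a patient-mix ratio, and the two outputs are then read as counts of MR-positive and MR-negative children.

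Sensitivity is estimated only in MR-positive children and specificity only in MR-negative children. In the specificity run, the 366 cases contribute nothing to specificity. This is the only power statement for the accuracy objective of a study described as pivotal, so the chance of success on either measure is in effect not stated.

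Two related gaps make this worse. Where the specialist's image reading is itself the reference, the specialist has no observed error rate to compare with. And a rule that asks only whether the result lies within the margin does not control the Type-I error unless it refers to a confidence limit.

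**Working it through.** **Inputs.** Prevalence 0.61, so λ = 0.39/0.61 = 0.639; accuracy 0.89 (sensitivity) and 0.87 (specificity) for both readers; d = 0.07; power 80%; Type-I error 5%. All are from Sample size determination.

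**1. Reproducing the plan's figures.** With equal accuracies the formula is N = (Zα + Zβ)² / d² × [p(1 − p) + p(1 − p)/λ], and the second group is λN. At one-sided 5%, (1.645 + 0.842)² = 6.183 before rounding of the Z values, and d² = 0.0049. Because 1 + 1/λ = 1/0.39, the bracket is p(1 − p)/0.39.

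- p = 0.87: bracket 0.1131/0.39 = 0.2900; N = 365.9 and λN = 233.9 (stated 366 and 234).
- p = 0.89: bracket 0.0979/0.39 = 0.2510; N = 316.7 and λN = 202.5 (stated 318 and 203, a difference of the size that rounding Z produces).
- With Zα = 1.960, p = 0.87 gives 464.5 and 297.0. The plan therefore used one-sided 5%.

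**2. What the 80% describes.** For 366 software readings against 234 ophthalmologist readings of a single proportion of 0.87:

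0.07 / √[0.87 × 0.13 × (1/366 + 1/234)] − 1.645 = 0.07/0.02815 − 1.645 = 0.842, which is 80% power.

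No such comparison exists in this study. Every child is imaged, and the software and the grader read the same images.

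**3. Power on the children who inform each measure.** Assumptions: one software result per child, true accuracy 0.89 and 0.87, fixed bars 0.89 − 0.07 = 0.82 (n = 366) and 0.87 − 0.07 = 0.80 (n = 234). Power is the binomial probability of reaching the smallest passing count. Joint power is the product, because the two measures use different children.

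| Rule | Sensitivity: count needed, power | Specificity: count needed, power | Both |
|---|---|---|---|
| Exact or Wilson two-sided 95% lower limit | 315/366, 96.6% | 200/234, 78.9% | 76.2% |
| Wald 95% lower limit | 314/366, 97.6% | 199/234, 83.9% | 81.9% |
| Jeffreys 95% lower limit | 315/366, 96.6% | 199/234, 83.9% | 81.0% |
| Exact one-sided 5% test | 313/366, 98.4% | 198/234, 88.0% | 86.6% |

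**4. The success rule read as a point-estimate rule.** The bars are 0.82 × 366 = 300.1, so 301 correct, and 0.80 × 234 = 187.2, so 188 correct.

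- P(X ≥ 301 | n = 366, true 0.82) = 48.5%.
- P(X ≥ 188 | n = 234, true 0.80) = 48.7%.
- A result that only just passes has an exact 95% lower limit of 0.779 for sensitivity and 0.747 for specificity, both below the 80% minimum that the plan cites.

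**5. If a direct comparison of readers were intended.** With both readers on the same children but independent errors, one-sided 5%, power = Φ(0.07/√[2p(1 − p)/n] − 1.645):

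- Sensitivity, n = 366: 0.07/0.02313 − 1.645 = 1.38, power 91.6%.
- Specificity, n = 234: 0.07/0.03109 − 1.645 = 0.61, power 72.8%.
- Both: 66.7%.

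With a paired analysis, power depends on the share of children on whom the readers disagree, which the plan does not give. At assumed discordance of 10%, 15% and 20%, power = Φ(0.07/√[ψ/n] − 1.645) is 95.9%, 86.9% and 77.3% for specificity, and 99.5%, 96.5% and 91.1% for sensitivity.

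**The case against.** The strongest reply is that nothing here shows a shortfall. The plan's arithmetic is right, the 600 is kept, and under the fixed-bar tests above single-measure power is close to or above 80%. On this view the plan has a badly derived justification for a workable number. That is true as far as it goes, but some analyses land near 80% by coincidence. Specificity power at 234 MR-negative children runs from 73% to 96% across the analyses in the working, and the plan does not say which one applies.

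A second reply is that a confidence limit is implied: the plan states a 5% Type-I error, speaks of a lower bound and promises 95% intervals. Part of this stands. Intervals are planned, and the 49% pass rate holds only if the rule is applied to point estimates. But the lower bound is presented as a consequence of accuracy minus margin, not as an interval limit, and the 95% intervals are not tied to the margin in the available text. A two-sided 95% interval also implies one-sided 2.5%, whereas the sizing used one-sided 5%. The missing part of the list in DATA ANALYSIS could bear on which comparisons are made. It does not affect the error in λ.

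A third reply is that testing against fixed bars replaces the reader comparison that the plan describes and lowers the Type-I error used for sizing. Both are fair, and the fix should say so. Moving from one-sided 5% to a 95% limit takes specificity power from 88% to 79% and joint power from 87% to 76%. If a reader comparison with independent errors is kept, specificity needs 286 MR-negative children, or 286/0.39, about 734 children in all. The statement that no extra patients are needed therefore applies to the fixed-bar test only.

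**Conclusion.** The concern holds and must be fixed. The stated 80% power applies to neither sensitivity nor specificity, because λ is a reader-group ratio filled with a prevalence ratio. The success rule names no confidence limit. Applied to point estimates, it would pass software lying exactly on either bar about 49% of the time on that measure.

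The finding does not show that 600 is too few. Against fixed bars of 0.82 and 0.80 with exact 95% lower limits, power is about 97% (sensitivity), 79% (specificity) and 76% (both). These figures assume 366 MR-positive and 234 MR-negative children with one usable software result each, true accuracy of 0.89 and 0.87, and the literature values taken as fixed. Per-camera analyses or rejected images would reduce the numbers available. Confidence in the error itself is high, since the plan's figures reproduce exactly this way for the run that sets the 600.

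**What to change.** Keep the planned 600, with at least 366 MR-positive and 234 MR-negative children, and change the text as follows.

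1. Replace the formula with a separate calculation for each measure: sensitivity on MR-positive children, specificity on MR-negative children.
2. Replace the success rule, and the matching hypothesis wording, with a test that names the interval method and its sidedness. Using the plan's own inputs: *The software meets the performance goal if the lower limit of the exact (Clopper-Pearson) two-sided 95% confidence interval is at least 0.82 for sensitivity (0.89 − 0.07) in MR-positive children and at least 0.80 for specificity (0.87 − 0.07) in MR-negative children. Both must be met.* State that this treats the literature values as fixed and replaces a direct comparison with readers.
3. Restate power at 366 and 234 as about 97%, 79% and 76% (both), and say openly that specificity and joint power are below 80%. If an exact one-sided 5% test is preferred, which matches the sizing already used, say so in DATA ANALYSIS, because 95% intervals are planned there, and report 98%, 88% and 87%.
4. If a direct comparison with ophthalmologists is kept, name a reference that is independent of the reader being compared. Base power only on children who have it: the Sampling procedure conditions provide for "when possible, a BIO (if available) conducted by an ophthalmologist", so that number may be well below 600. State the assumed agreement between readers. Until these are given, power for that comparison can only be shown as a range under assumptions.

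**Cost.** Rewriting the sample-size section, the hypothesis sentence and the success rule, and adding one sentence to DATA ANALYSIS. Restating power at 600 needs no extra patients; a retained reader comparison might.

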To answer *study question #2*, sensitivity and specificity with 95% CI will be calculated for each of the following:

- presence or absence of MR (any hemorrhage, whitening or abnormal vessels) between:

To answer *study question #3*, positive predictive value (PPV) and negative predictive value (NPV) will be calculated to evaluate software algorithm’s performance in classifying a retinal image for presence or absence of each of the following MR lesions, against retinal grader’s grading for the presence of respective lesions.

The analyses described above will be performed for subgroups determined by malaria test results as well. It is not possible to mask the malaria status from the examining clinicians. The analysis results will be presented in form of tables.

DISSEMINATION OF THE RESULTS

Results of the study will be provided to VisionQuest Biomedical and NHERC in the final report, presented locally in Nigeria, and submitted to an international journal for publication. Standard rules for authorship on a final publication will apply.

A copy of the final report and any published paper(s) or abstracts of papers read at conferences out of the research findings will be submitted to each of the following:

1. VisionQuest Biomedical Inc.
2. University College Hospital, Ibadan, Nigeria
3. Amino Kano University, Kano
4. General Sani Abacha Specialist Hospital Damaturu
5. State Specialist Hospital Sokoto -
6. Massey's Children Hospital, Lagos Island

A copy of the data (including photos) will be distributed to all of the above institutions, if necessary, for use in future analysis upon agreement of the main investigators.

ETHICAL CONSIDERATIONS

Study personnel trained in human ethics will obtain informed consent from parents of study participants. The Principal and co-investigators will conduct on-site training sessions for Nigerian study staff who will be collecting study information and obtaining

consent from study participants. The study will be explained in detail to the local study staff. The basic principles of informed consent process, documentation of informed consent, protection of subjects' rights, confidentiality, and handling of data will be covered in these training sessions. All training sessions will be documented, and study staff monitored by the on-site project manager on a regular basis to ensure compliance with the principles of informed consent.

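### The success rule names no confidence limit; followed as written, it passes software sitting at the non-inferiority margin on one measure about 49% of the time, against a stated 5%

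*Combined protocol and SAP*

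**What the plan says.** All of this is in the Methodology chapter of the combined protocol and SAP.

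- **Hypothesis (Sample size determination).** Sensitivity and specificity of the software are to be "non-inferior to the clinical reference standard, which is defined as the reading of retinal images for MR detection by ophthalmic specialists".
- **Non-Inferiority test design.** Specialist accuracy is taken from the literature as 89% sensitivity and 87% specificity, with a margin of 7 points. The normal quantiles in the Blackwelder formula "are standard values assuming 80% power and 5% Type-I error"; sidedness is not given. The same section infers from the margin that "the lower-bound on both sensitivity and specificity will be at least equal or greater than the minimum sensitivity and specificity requirements" of 80% and 80%, without saying what kind of bound is meant or at what level.
- **Check of the sample size.** The calculation was verified with an R package that "includes a function to calculate the sample size needed for two sample non-inferiority test".
- **Conclusion.** The requirement is 366 MR-positive and 234 MR-negative children. The sponsor will then "validate the software-based test performance on the collected sample and verify if the resulting sensitivity/specificity is within the margin of difference". The next sentence draws the inference: "Upon verification, it can be concluded that the experimental test is non-inferior to the standard test within a non-inferiority margin of 7" per cent.
- **Data Analysis.** For study question 2, "sensitivity and specificity with 95% CI will be calculated for each of the following". In the text available, these intervals are not compared with the margin or tied to a decision. The list that should follow is missing from that text.

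**The concern.** A non-inferiority claim needs the confidence limit, not the estimate, to clear the margin. The Conclusion checks only the resulting sensitivity and specificity. A rule based on the estimate passes about half the time when the truth lies exactly on the margin, whatever the sample size, so the 5% error used to size the study is not delivered.

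If a confidence limit was meant, the analyst must still choose the test, the level and the sidedness after seeing the data, and the pass mark depends on that choice. The comparator is unsettled too: the sample size treats specialist accuracy as a second estimated proportion, the margin arithmetic treats 89% and 87% as constants, and the hypothesis makes the specialist reading itself the reference standard.

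The protocol calls the study pivotal, and this rule decides its main claim. High specificity is the property the protocol relies on to prevent deaths from misdiagnosed cerebral malaria.

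**Working it through.** **Inputs.** From the sample size section: standard and software sensitivity both 0.89, standard and software specificity both 0.87, margin 0.07, prevalence 0.61, type I error 5%, power 80%, planned numbers 366 and 234. The limits 0.89 − 0.07 = 0.82 and 0.87 − 0.07 = 0.80 are derived; the only minimum printed in the plan is 80%/80%.

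**1. Reproduce the plan's sample size.** With equal accuracies p and λ = 0.39/0.61, the printed formula becomes

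N(cases) = (Zα + Zβ)² / 0.07² × p(1 − p) × (1 + 1/λ), and N(controls) = λ × N(cases), where 1 + 1/λ = 2.564.

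| Inputs | (Zα + Zβ)² | Cases | Controls | Plan |
|---|---|---|---|---|
| p = 0.89, one-sided 5% | (1.645 + 0.842)² = 6.18 | 316.7 | 202.5 | 318 / 203 |
| p = 0.87, one-sided 5% | 6.18 | 365.9 | 233.9 | 366 / 234 |
| p = 0.87, one-sided 2.5% | (1.960 + 0.842)² = 7.85 | 464.5 | 297.0 | no match |

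The plan's numbers therefore assume a one-sided 5% test. The level matching a two-sided 95% interval would need about 762 children, not 600.

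**2. Pass probability of the rule as written.** The smallest counts that meet it are 301 (0.82 × 366 = 300.1) and 188 (0.80 × 234 = 187.2). Exact binomial tails:

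- P(X ≥ 301 | 366, 0.82) = 0.485
- P(X ≥ 188 | 234, 0.80) = 0.487

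Both measures must pass. With sensitivity at 0.82 and specificity at 0.87, the overall pass rate is 0.485 × 0.998 = 0.484. With specificity at 0.80 and sensitivity at 0.89, it is 0.487. With both at their limits, and assuming independence, it is 0.485 × 0.487 = 0.236.

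Below the limits, with the other measure well above its own:

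- sensitivity 0.80 (the printed minimum): P(X ≥ 301 | 366, 0.80) = 0.157
- specificity 0.78: P(X ≥ 188 | 234, 0.78) = 0.218

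**3. The other reading of the word difference.** Suppose the observed software value is compared with an observed specialist value from independent readings. With the software truly 7 points worse, it passes 49.5% to 49.8% of the time on sensitivity (366 against 366, or 366 against 234) and 50.6% on specificity (234 against 234).

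**4. A rule based on the confidence limit, with fixed references.** Clopper-Pearson lower limits:

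| Rule | Sensitivity needs | Error at 0.82 | Power at 0.89 | Specificity needs | Error at 0.80 | Power at 0.87 | Both pass* |
|---|---|---|---|---|---|---|---|
| One-sided 95% limit | 313/366 | 4.3% | 98.4% | 198/234 | 4.3% | 88.0% | 86.6% |
| Lower end of two-sided 95% CI | 315/366 | 2.3% | 96.6% | 200/234 | 1.9% | 78.9% | 76.2% |

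*Assuming independence.

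**5. A concurrent comparison with specialists.** For unpaired readings with equal true accuracy and one-sided 5%, power = Φ(0.07 / √(2p(1 − p)/n) − 1.645).

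- Sensitivity, p = 0.89, n = 366: Φ(3.026 − 1.645) = 91.6%
- Specificity, p = 0.87, n = 234: Φ(2.251 − 1.645) = 72.8%
- For 80% power on specificity: n = 6.18 × 2 × 0.87 × 0.13 / 0.07² = 285.4, so 286 MR-negative children

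If the same children are read both ways, the standard error is √(discordance/n). The plan gives no discordance. Over an assumed range of 10% to 20%, specificity power with 234 children is 95.9% to 77.3%.

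**The case against.** The best defence is that the Conclusion should not be read alone. The plan declares a non-inferiority design, states a 5% error, speaks of a lower bound and plans 95% confidence intervals, so a confidence-limit comparison was probably intended. That may be so, but no sentence states it. The lower-bound remark gives no level and follows directly from the margin, so it reads as the subtraction that yields 82% and 80%. The planned 95% intervals have no stated role in the decision, and using them would not match the one-sided 5% sizing.

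It can also be said that the cut-offs 301 and 188 belong to one reading, because a margin of difference may refer to specialists read alongside the software. That is fair, but the pass rate under that reading is still about 50%.

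Two points do stand. First, a pass rate near one half is what any rule based on the estimate gives at its own boundary; the figure shows the kind of rule, not a flaw peculiar to these sample sizes. Second, where the specialist reading is both comparator and reference standard, a confidence limit alone does not make the comparison estimable. The comparator has to be settled as part of the fix.

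**Conclusion.** The concern holds, and the rule must be corrected before the data are analysed. As written, it gives a false-pass rate of 48.5% (sensitivity at 82%) or 48.7% (specificity at 80%) when the other measure is well above its limit, and 23.6% when both are at their limits, against a stated 5%. The intent may have been sound, but the plan does not say so, and the more charitable reading leaves the pass mark to be chosen later (313 or 315 of 366; 198 or 200 of 234).

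These figures assume exactly 366 and 234 evaluable children, one software result per child, both measures required, and independence wherever a joint probability is given.

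**What to change.** Decide first whether 89% and 87% are fixed reference values or are to be estimated from concurrent specialist readings. If they are fixed, replace the verification sentence in the Conclusion with:

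> The values 89% and 87% are treated as fixed reference values. Non-inferiority is concluded only if the one-sided 95% exact lower confidence limit (the lower end of the two-sided 90% interval) exceeds 82% for sensitivity and exceeds 80% for specificity.

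Keep the 95% intervals in Data Analysis for reporting. This version adds no patients, provided 366 and 234 children are evaluable. The claim becomes harder to win: 313 and 198 correct results instead of 301 and 188, with 86.6% power for both measures together.

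If the lower end of the two-sided 95% interval is to be the test, say so and restate power. Specificity falls to 78.9%, just under the stated 80%, and joint power to 76.2%.

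If a concurrent comparison is intended, require the lower confidence limit of the difference (software minus specialist) to lie above −7 points for each measure, name a reference other than that same specialist reading, and restate power. Unpaired, specificity would need about 286 MR-negative children instead of 234 for 80% power. Paired, the requirement depends on a discordance rate that the plan would have to assume and justify.
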